To evaluate the persistence of vaccine-induced serum anti-HPV 6, anti-HPV 11, anti-HPV 16 and anti-HPV 18 responses, GMTs and the proportions of subjects with anti-HPV ≥ 200 mMU/mL for each vaccine HPV type will be summarized at Month 7, Month 24, and Month 48. Graphical displays of the distribution of titers among subjects administered each lot of the quadrivalent HPV (Types 6, 11, 16, 18) L1 VLP vaccine will be provided by HPV type.

C. **Approaches to Immunogenicity Analysis (Cont.)**

3. **Exploratory Immunogenicity Analyses**

a. **Immune Responses to Each Vaccine HPV Type in Subjects Who Are Baseline Seropositive for the Given Type**

Assessments in this section will be performed only when data permits; that is, when the number of subjects in the subgroup being analyzed is sufficient.

To explore a potential association between baseline seropositivity for a given vaccine HPV type and improved Postdose 3 immunogenicity for the same HPV type (immune memory), the proportions of subjects with anti-HPV ≥ 200 mMU/mL and the GMTs at Month 7 for each vaccine HPV type will be summarized in subjects who are seropositive at Day 1 for that vaccine HPV type (6, 11, 16, or 18), regardless of PCR status. The responses will be compared observationally with the proportions of subjects with anti-HPV ≥ 200 mMU/mL and the GMTs at Month 7 in (1) subjects who are seronegative at Day 1 and PCR-negative from Day 1 through Month 7 for the vaccine HPV type of interest and (2) subjects who are seronegative at Day 1 and PCR-negative from Day 1 through Month 7 for all vaccine types. RCDF (Reverse Cumulative Distribution Function) plots will also be used to observationally compare these groups. These summaries will evaluate the anamnestic responses to the individual components of the quadrivalent HPV (Types 6, 11, 16, 18) L1 VLP vaccine. Table 2 outlines the groups that will be compared for this analysis.

Table 2

Comparisons to Assess a Potential Association Between Baseline Seropositivity and Improved Immunogenicity at Month 7

Comparison Group 1	Comparison Group 2
HPV type 6 sero+ at Day 1 [†]	HPV type 6 naïve [‡]
HPV type 6 sero+ at Day 1 [†]	Naïve for all vaccine HPV types [‡]
HPV type 11 sero+ at Day 1 [†]	HPV type 11 naïve [‡]
HPV type 11 sero+ at Day 1 [†]	Naïve for all vaccine HPV types [‡]
HPV type 16 sero+ at Day 1 [†]	HPV type 16 naïve [‡]
HPV type 16 sero+ at Day 1 [†]	Naïve for all vaccine HPV types [‡]
HPV type 18 sero+ at Day 1 [†]	HPV type 18 naïve [‡]

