HPV type 18 sero+ at Day 1 [†]	Naïve for all vaccine HPV types [‡]
Comparisons will be made between Group 1 and Group 2.	
Sero+ = Seropositive.	
[†] Regardless of PCR status.	
[‡] Naïve = Seronegative at Day 1 and PCR negative from Day 1 through Month 7.	

C. Approaches to Immunogenicity Analysis (Cont.)

To investigate whether or not the baseline titer of a subject who is seropositive at Day 1 for a given vaccine HPV type has an impact on the subject's response to the vaccine at Month 7, the natural log of the Month 7 titers for a given HPV type will be modeled as a function of treatment group and the natural log of the baseline HPV titer for that same HPV type for subjects who are seropositive for that HPV type at baseline. Three regression models will be constructed. The first will be a linear regression model with the natural log titers at Month 7 as the response variable. The second will be a logistic regression model with an indicator of whether or not the subject's Month 7 titer is ≥ 200 mMU/mL as the response variable. The third will be a linear regression model with the difference in natural log titer between Month 7 and Day 1 as the response variable (this model is equivalent to modeling the fold-rise in titer from Day 1 to Month 7).

The study will also explore whether subjects who are HPV infected but who do not have detectable anti-HPV at baseline have an active immune response to the infection. In particular, peak (Month 7) and persistence anti-HPV responses for a given vaccine HPV type will be compared between subjects who are infected at Day 1 (PCR positive) with that HPV type, but who have not developed a detectable anti-HPV response (seronegative) to that type, and those who are naïve for that HPV type. It is assumed that newly infected subjects are PCR positive but still have negative RIA titers. Therefore, the antibody responses in subjects who are initially PCR positive but seronegative for a given vaccine HPV type will be summarized and compared observationally with subjects who are HPV-naïve for that HPV type and with subjects who are HPV-naïve for all vaccine HPV types (naïve implies seronegative at Day 1 and PCR-negative from Day 1 through Month 7). The GMTs and the proportions of subjects with anti-HPV ≥ 200 mMU/mL at Month 7 and through the persistence phase will be summarized. Table 3 outlines the groups that will be compared for this analysis.

C. Approaches to Immunogenicity Analysis (Cont.)

Table 3

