The exploratory analysis of the association among vaccine HPV types has 2 goals: (1) to ascertain if seropositivity for one HPV type impacts the immune response to another vaccine HPV type and (2) to assess whether or not the magnitude of the association appears to increase by the number of other vaccine HPV types for which the subject is positive.

To assess whether or not baseline seropositivity for 1 vaccine HPV type impacts the immune response to another vaccine HPV type, the GMTs and the proportions of subjects with anti-HPV ≥ 200 mMU/mL at Month 7 for a given vaccine HPV type will be observationally compared between subjects who are HPV naïve for all vaccine HPV types from Day 1 to Month 7 and subjects who are HPV naïve for the given vaccine HPV type but seropositive for each 1 of the other 3 vaccine HPV types individually. For example, the HPV 6 immune responses will be summarized and compared between subjects who are HPV naïve for all vaccine HPV types from Day 1 to Month 7 and: (1) subjects who are naïve for HPV type 6 from Day 1 to Month 7 but seropositive to HPV type 11 at Day 1; (2) subjects who are naïve for HPV type 6 from Day 1 to Month 7 but seropositive to HPV type 16 at Day 1; and (3) subjects who are naïve for HPV type 6 from Day 1 to Month 7 but seropositive to HPV type 18 at Day 1. RCDF plots will also be used to compare these groups. Table 5 outlines the groups that will be compared for this analysis.

C. Approaches to Immunogenicity Analysis (Cont.)

Table 5

Comparisons to Assess the Impact of Baseline Seropositivity for One Vaccine HPV Type on the Immune Responses to Another Vaccine HPV Type

HPV Type to be Summarized	Comparison Group 1	Comparison Group 2
6	Baseline sero+ for HPV type 11 [†] Baseline sero+ for HPV type 16 [†] Baseline sero+ for HPV type 18 [†]	Vaccine HPV type naïve [‡] Vaccine HPV type naïve [‡] Vaccine HPV type naïve [‡]
11	Baseline sero+ for HPV type 6 [†] Baseline sero+ for HPV type 16 [†] Baseline sero+ for HPV type 18 [†]	Vaccine HPV type naïve [‡] Vaccine HPV type naïve [‡] Vaccine HPV type naïve [‡]
16	Baseline sero+ for HPV type 6 [†] Baseline sero+ for HPV type 11 [†] Baseline sero+ for HPV type 18 [†]	Vaccine HPV type naïve [‡] Vaccine HPV type naïve [‡] Vaccine HPV type naïve [‡]
18	Baseline sero+ for HPV type 6 [†] Baseline sero+ for HPV type 11 [†] Baseline sero+ for HPV type 16 [†]	Vaccine HPV type naïve [‡] Vaccine HPV type naïve [‡] Vaccine HPV type naïve [‡]

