Comparisons will be made between Group 1 and Group 2. Sero+ = Seropositive. [†] HPV seronegative at Day 1 and PCR negative from Day 1 through Month 7 for all other vaccine HPV types. [‡] Seronegative at Day 1 and PCR negative from Day 1 through Month 7 for all vaccine HPV types.		

Finally, to explore the impact of multiple positive vaccine HPV types on immune responses to the other vaccine HPV types, the proportions of subjects with anti-HPV ≥ 200 mMU/mL and the GMTs at Month 7 for a given vaccine HPV type will be summarized and compared between subjects who are HPV naïve for all vaccine HPV types from Day 1 to Month 7 and: (1) subjects who are seronegative at Day 1 for the HPV type being summarized but who are seropositive at Day 1 for all possible combinations of 2 of the other 3 vaccine HPV types and (2) subjects who are seronegative at Day 1 for the HPV type being summarized but who are seropositive at Day 1 for all 3 of the other vaccine HPV types. Table 6 provides all summaries that will be performed for this purpose.

Data permitting, the question of associations among the vaccine HPV types will be explored with regression models. The first set of models will explore the individual associations between HPV vaccine types. The first model will model the Month 7 responses for 1 vaccine HPV

C. Approaches to Immunogenicity Analysis (Cont.)

type (e.g., HPV type 6) as a function of the baseline titers for the other 3 vaccine HPV types (e.g., HPV type 11, 16, and 18). The second model will model the Month 7 responses for 1 vaccine HPV type (e.g., HPV type 6) as a function of the Month 7 responses for the other 3 vaccine HPV types (HPV types 11, 16, or 18). These models will be constructed separately for subjects who are: (1) seronegative for the HPV type of interest and (2) seropositive for the HPV type of interest at Day 1.

An additional model will assess the impact of the number of vaccine HPV types for which the subject is positive at baseline on the response to a different given HPV type. This model will model the Month 7 responses for one vaccine HPV type (e.g., HPV type 6) as a function of the number of other vaccine HPV types that are seropositive at Day 1 (0, 1, 2, or 3 seropositive titers among the set of HPV types 11, 16, and 18).

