Linear regression models will be used with the natural log of the Month 7 titers as the response variable. The exploratory immunogenicity analyses will be performed on the per-protocol population. Due to possible sample size limitations, all comparisons between groups will be observational, and some assessments may not be viable due to small cell sizes.

C. Approaches to Immunogenicity Analysis (Cont.)

Table 6

Comparisons to Explore the Impact of Multiple Baseline Positive Vaccine HPV Types on the Immune Responses to the Other Vaccine Types

HPV Type to be Summarized	Comparison Group 1	Comparison Group 2
6	Sero- for HPV 6 but sero+ for 2 of vaccine HPV types 11, 16, and/or 18	Vaccine HPV type naïve [†]
	Sero- for HPV 6 but sero+ for HPV types 11, 16, and 18	Vaccine HPV type naïve [†]
11	Sero- for HPV 11 but sero+ for 2 of vaccine HPV types 6, 16, and/or 18	Vaccine HPV type naïve [†]
	Sero- for HPV 11 but sero+ for HPV types 6, 16, and 18	Vaccine HPV type naïve [†]
16	Sero- for HPV 16 but sero+ for 2 of vaccine HPV types 6, 11, and/or 18	Vaccine HPV type naïve [†]
	Sero- for HPV 16 but sero+ for HPV types 6, 11, and 18	Vaccine HPV type naïve [†]
18	Sero- for HPV 18 but sero+ for 2 of vaccine HPV types 6, 11, and/or 16	Vaccine HPV type naïve [†]
	Sero- for HPV 18 but sero+ for HPV types 6, 11, and 16	Vaccine HPV type naïve [†]
Comparisons will be made between Group 1 and Group 2. Sero- = Seronegative. Sero+ = Seropositive. [†] Seronegative at Day 1 and PCR negative from Day 1 through Month 7 for all vaccine HPV types.		

D. Definition of Compliance Measure

In the consistency lot substudy, the numbers and percentages of subjects who complete each vaccination visit and who complete the follow-up blood sampling at Month 7 will be summarized by treatment group (consistency lot) and in total.

V. SAFETY ANALYSES

All subjects who received at least 1 injection and have follow-up data will be included in the summary of serious adverse experiences. All subjects in the NSAE substudy and in the United Kingdom who received at least 1 injection and have follow-up data will be included in the safety summaries of nonserious

V.SAFETY ANALYSES (CONT.)

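### In subjects seropositive for the type of interest, the exploratory cross-type regressions omit that type's own Day 1 titer, so own-type memory can be reported as a cross-type effect

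*SAP*

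**What the plan says.** The first goal of SAP section IV.C.3.b (Association Among Vaccine HPV Types) is "to ascertain if seropositivity for one HPV type impacts the immune response to another vaccine HPV type". Three regressions serve the section, data permitting:

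- **Baseline-titer model:** the Month 7 response for one type "as a function of the baseline titers for the other 3 vaccine HPV types".
- **Month 7 model:** the same response "as a function of the Month 7 responses for the other 3 vaccine HPV types".
- **Count model:** the same response "as a function of the number of other vaccine HPV types that are seropositive at Day 1".

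The first two are fitted in two groups, the second being "2) seropositive for the HPV type of interest at Day 1". No such split is stated for the count model. On the form of the models, the section says: "Linear regression models will be used with the natural log of the Month 7 titers as the response variable".

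Section IV.C.3.a deals with the own-type question. It looks for an association between baseline seropositivity and "improved Postdose 3 immunogenicity for the same HPV type (immune memory". In subjects seropositive for a type it models the Month 7 titer on treatment group and "the natural log of the baseline HPV titer for that same HPV type". The other three types are not in that model.

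**The concern.** Splitting by own-type serostatus fixes positive versus negative. It does not fix the level of the own-type titer among the positives. In that group the SAP itself thinks the own-type titer may drive the Month 7 response, but the cross-type models do not include it, and the own-type model does not include the other types. No planned model contains both.

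A non-zero coefficient for another type can then mean either of two things: that type affects the response, or its titer stands in for the own-type titer. In this group the unadjusted model cannot tell enhancement or interference between types from own-type memory, although separating them is the stated purpose.

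**Working it through.** **Plan's own figure.** The SAP gives no slope, titer correlation or error rate for these models, so there is nothing to reproduce directly. The size below rests on assumptions.

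**What the SAP implies about dependence between types.** Section VII.A.1 assumes about 18% positive for HPV 16, 18% for HPV 18 and an overlap of about 8%.
- 11,500 × 0.85 = 9,775 after attrition. Then 9,775 × 0.82 = 8,016 (SAP: ~8000) and 9,775 × 0.92 = 8,993 (SAP: ~9000). The 8% therefore means positive for both.
- Independence would give 0.18 × 0.18 = 3.2%.
- Cells: both 8%, one only 10% and 10%, neither 72%. Odds ratio = (0.08 × 0.72)/(0.10 × 0.10) = 5.8.

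Positivity is therefore assumed to cluster. But this is positivity by serology or PCR in all enrolled subjects, not titer among the seropositive, so it does not supply the correlation needed below.

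**Size of the seropositive group.** 1,500 × 0.85 × 0.18 = 229.5, so about 230 at most, because the 18% includes subjects positive by PCR only. Group sizes of 30, 60 and 130 were used.

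**Model.** All four baseline log titers are standardized, with common correlation ρ. Month 7 log titer = b × own-type titer + error with SD 1. The true effect of every other type is zero. Assumed: b = 0.5, ρ = 0.5.

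**Bias when own-type titer is omitted.**
- Each of the three coefficients has expectation bρ/(1 + 2ρ) = 0.25/2 = 0.125 instead of 0.
- The three other types explain R² = 3ρ²/(1 + 2ρ) = 0.75/2 = 0.375 of the own-type titer.
- Residual variance = 1 + b²(1 − R²) = 1 + 0.25 × 0.625 = 1.156.
- Variance inflation from correlation among the three = (1 + ρ)/[(1 − ρ)(1 + 2ρ)] = 1.5/(0.5 × 2) = 1.5.
- Standard error ≈ √(1.156 × 1.5/n). At n = 130 this is 0.1155, so the coefficient sits 0.125/0.1155 = 1.08 standard errors from zero and is declared significant in about 19% of trials. The same formula gives about 11% at n = 60 and 8% at n = 30.
- Joint test of the three, non-centrality n b²R²/1.156 = 0.081n: 2.4, 4.9 and 10.5.

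**Simulation, two-sided 5%.**

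| n | One coefficient, as written | Joint test, as written | Either, own-type titer added |
|---|---|---|---|
| 30 | 8% | 19% | about 4-6% |
| 60 | 10% | 42% | about 4-6% |
| 130 | 18% | 77% | about 4-6% |

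An independent run gave the same single-coefficient rates and 20%, 38% and 75% for the joint test. Over slopes of 0.3-0.5, correlations of 0.3-0.5 and n from 30 to 230, the joint rate ran from 7% to 96%.

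**Boundary.** With b = 0 or ρ = 0, the bias bρ/(1 + 2ρ) is zero and the error rate stays at its nominal level.

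The Month 7 model and the count model were not simulated.

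**The case against.** The case on the other side has several parts.

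- **Both conditions are unproven.** The SAP only explores the own-type effect and is silent on titer correlation among the seropositive. This stands. It is why the conclusion is that misattribution can happen, not that it does. Selection may also weaken the correlation: if 0.5 is the correlation before selection and 15% are seropositive (assumed), it falls to about 0.2 in the group, and the single-coefficient rates to 7%, 8% and 12%.
- **Larger rates do not belong to this plan.** A reader might work with one other type in the model, which under the same slope and correlation gives 22%, 44% and 73%. The SAP enters three types together, so the bias is shared and each coefficient is less affected. Only the joint test comes near those figures.
- **A reader might infer that the whole cross-type question is compromised.** The SAP does not support that. Table 5 compares subjects naïve for the type summarized, Table 6 uses subjects seronegative for it, and the regressions are also fitted in own-type seronegatives. None of these has this problem.
- **The analysis is exploratory,** depends on data permitting, and has no decision rule. This stands and keeps the priority low.
- **Adjustment may change the question.** All baseline titers are taken on the same day. If exposure to another type raises the measured own-type titer, adjustment removes part of the cross-type association. This is fair, and a reason to show both models. It does not rescue the unadjusted model alone, because the goal is worded as impact rather than mere association.

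**Conclusion.** The point holds as a low-priority defect in one part of an exploratory analysis. In subjects seropositive for the type of interest, the baseline-titer model omits a confounder that the SAP itself names, and no other planned model separates the two effects. Whether this misleads depends on an own-type slope and a within-group titer correlation, both needed and neither given. The rates in the table illustrate one assumed pair of values; they do not predict what this trial will show. The seronegative-group models, Tables 5 and 6, and all primary and secondary conclusions are unaffected.

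**What to change.** - In the baseline-titer model for subjects seropositive for the type of interest, add the natural log of that type's own Day 1 titer. The unadjusted model may be shown beside it.
- Split the count model by own-type serostatus, with own-type log Day 1 titer as a covariate in the seropositive part.
- In the same edit, state which population supplies the seropositive group. Section IV.C.3.b assigns these analyses to the per-protocol population, which requires seronegativity to the appropriate types; read strictly, that would leave the group empty.

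The titer is already collected and already used in IV.C.3.a. The cost is one degree of freedom per adjusted model and a few lines of SAP text. For the Month 7 model, adding the own-type titer would not be a full answer, since general responsiveness to vaccination could still link Month 7 titers across types.

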adverse experiences. In all summaries, subjects who are incorrectly randomized will be summarized for safety according to the clinical material they received. If a subject received vaccine at any of the visits, then the subject will be summarized in the appropriate vaccine group. Subjects will be summarized in the placebo group only if they received placebo at all visits.

For the nonserious adverse experience summaries, the data from the NSAE substudy and the data from the subjects in the United Kingdom will be summarized separately and combined. Separate summaries will be provided because the differences in the nonserious adverse experience reporting mechanisms in the 2 sets of subjects (vaccination report card in the NSAE substudy versus solicitation at the next visit in the United Kingdom) may lead to differences in the adverse experience rates. In particular, without the written reminders from the vaccination report cards, the subjects in the United Kingdom may be susceptible to recalling only the more significant adverse experiences when they are asked for adverse experience data at the next visit (which will likely be 2 to 4 months following the previous vaccination).

Subjects enrolled at study sites outside of the United States and the United Kingdom may report nonserious adverse experiences spontaneously even though solicitation of such events is not a part of the adverse experience follow-up at these study sites. Any nonserious adverse experiences reported by subjects outside of the United States and the United Kingdom will be listed. Incidence rates among these subjects will not be estimated due to the difficulties in associating a correct denominator with data of this type (spontaneously reported).

The summaries of serious adverse experiences will be provided both for the vaccine groups pooled versus placebo and for the 3 consistency lots separately. However, since only ~650 subjects are expected to be enrolled into both the consistency lot substudy and NSAE substudy, the primary focus of the nonserious adverse experience safety summaries will be on comparisons between the placebo recipients and the pooled vaccine recipients. Nonserious adverse experience data will be tabulated by consistency lot to allow an observational assessment of the comparability of the safety profiles across lots.

A. Special Safety Analysis

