The primary endpoint for safety is the incidence of vaccine-related serious adverse experiences. Point estimates of the incidence of serious adverse experiences and vaccine-related serious adverse experiences and the corresponding 95% confidence intervals will be provided for each treatment group for all subjects enrolled in the study.

A. Special Safety Analysis (Cont.)

Severe injection site reactions are also of special interest. Therefore, for all subjects enrolled in the NSAE substudy and in the United Kingdom, point estimates of the incidences of severe injection site reactions will be provided for each treatment group along with the corresponding 95% confidence intervals.

For all subjects enrolled, pregnancies that occur during the study and their outcomes will be tabulated by treatment group and overall. Pregnancies that were detected anytime between Day 1 and 1 month following the completion of the vaccination regimen (Month 7) will be summarized separately from those detected following Month 7. In addition, the outcomes of all breast-feeding experiences in subjects who were breast-feeding during the vaccination regimen will be tabulated by treatment group and overall.

B. Adverse Experiences

To reduce the number of statistical tests performed for adverse experiences and the accompanying multiplicity issues associated with them, the following approach will be used for the analyses of adverse experiences. These analyses will be performed using the subset of subjects participating in the NSAE substudy only.

To provide an overall assessment of safety, measures such as the incidence of: (1) any adverse experience, (2) any injection-site adverse experience, (3) any systemic adverse experience, and (4) any vaccine-related adverse experience that occurred throughout the study will be summarized.

To address specific adverse experiences, the incidences of injection-site adverse experiences Days 1 to 5 and specific systemic adverse experiences within 14 days postvaccination occurring in at least 1% of the subjects will be tabulated across injections. Risk differences will be estimated, and the associated 95% two-sided confidence intervals will be provided. The method of Miettinen and Nurminen [1] will be used for all comparisons.

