Statistical testing will be conducted for the specific adverse experiences for which subjects were prompted on the vaccination report card. Therefore, the proportions of subjects who experience redness, swelling, and pain/tenderness at the injection site and the proportions of subjects with elevated temperatures ($\geq 100^{\circ}\text{F}$, oral equivalent) will be formally analyzed. In addition to the count and the percentage, the risk difference, the associated 95% confidence interval, and the two-sided p-value testing for a difference in incidence rates will be presented.

B. Adverse Experiences (Cont.)

Separate summaries will be performed for subjects who are: (1) seronegative at Day 1 and PCR-negative Day 1 through Month 7 to all 4 vaccine components, and (2) seropositive at Day 1 or PCR-positive at any time between Day 1 and Month 7 to at least 1 vaccine component. Tabulations of adverse experience data by injection will also be provided.

The distribution of adverse experiences across severity/intensity ratings will also be provided for each treatment group across all injections. Each episode of each reported adverse experience will be counted separately for this summary. The summary will be provided for any adverse experiences, any systemic adverse experiences, and any injection-site adverse experiences. For the measured adverse experiences of redness and swelling, 0 to 1 inch will be categorized as mild, >1 inch but ≤ 2 inches will be categorized as moderate and >2 inches will be categorized as severe. In addition, the distribution of injection-site adverse experiences will be summarized separately by adverse experience for the “prompted” adverse experiences of pain/tenderness/soreness, redness, and swelling.

To complement the analyses above, the number of subjects reporting an adverse experience within each severity/intensity category will be summarized across all adverse experiences reported. Each subject will be counted only once in these summaries. The worst severity/intensity rating will be utilized for each subject. These summaries will be performed for any adverse experiences, any injection-site adverse experiences, and any systemic adverse experiences. The summaries will be provided for each treatment group across all injections.

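### SAP Section V.A gives no interval for the vaccine-placebo difference on the primary safety endpoint, only a separate interval for each group

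*SAP*

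**What the plan says.** **Endpoint.** Section V.A states: "The primary endpoint for safety is the incidence of vaccine-related serious adverse experiences". The Executive Summary (Endpoints, Safety) also lists severe injection-site adverse experiences among the primary safety variables.

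**Planned statistic.** For serious and vaccine-related serious adverse experiences, V.A plans point estimates, and "corresponding 95% confidence intervals will be provided for each treatment group for all subjects enrolled in the study". For severe injection-site reactions in NSAE and United Kingdom subjects, "point estimates of the incidences of severe injection site reactions will be provided for each treatment group along with the corresponding 95% confidence intervals". Neither sentence names a difference or a ratio.

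**Side-by-side display.** The opening of Section V adds: "The summaries of serious adverse experiences will be provided both for the vaccine groups pooled versus placebo and for the 3 consistency lots separately". It also sets the groups: a subject who received vaccine at any visit counts as vaccine, and only subjects given placebo at every visit count as placebo.

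**Where a difference is planned.** Section V.B says: "Risk differences will be estimated, and the associated 95% two-sided confidence intervals will be provided", by the Miettinen-Nurminen method. Two limits apply: "These analyses will be performed using the subset of subjects participating in the NSAE substudy only", and the events are specific injection-site (Days 1 to 5) and systemic (14-day) adverse experiences "occurring in at least 1% of the subjects will be tabulated across injections". P-values are narrower still: "Statistical testing will be conducted for the specific adverse experiences for which subjects were prompted on the vaccination report card".

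**The concern.** The trial randomizes about 11,500 subjects 1:1 against placebo and collects serious adverse experiences in all of them. The question a reader brings to the primary safety endpoint is how large an excess risk the data allow. A per-group interval describes how precisely one incidence is known. It does not say how precisely the difference is known. The plan specifies the right tool, a risk difference with a score interval, but applies it to common events in roughly a tenth of the subjects and not to the endpoint it calls primary.

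What is at stake is the completeness of the safety report. There is also a smaller gain from fixing the contrast before unblinding, so that it is not chosen afterwards. No efficacy result, error rate or sample size depends on it.

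**Working it through.** **1. Does another section supply the contrast?** The safety provisions of the SAP, set side by side:

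| Section | Events | Subjects | Between-group output |
|---|---|---|---|
| V, opening text | Serious | All with an injection and follow-up | Pooled vaccine and placebo shown together; no contrast named |
| V.A | Serious; vaccine-related serious | All enrolled | Incidence and 95% CI per group only |
| V.A | Severe injection-site reactions | NSAE and UK | Incidence and 95% CI per group only |
| V.B | Specific injection-site and systemic events in at least 1% | NSAE only | Risk difference with 95% CI |
| V.B | Report-card-prompted events | NSAE only | Risk difference, 95% CI and p-value |
| VI.B | Safety summaries for the DSMB | All available data | Frequencies and percentages by group |
| VII.E | Safety comparisons | n/a | Only a note that multiplicity is not adjusted |

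None gives a vaccine-placebo difference with an interval for serious events or for the severe category of injection-site reactions.

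**2. Do per-group intervals stand in for an interval on the difference?** The SAP states no rate, margin or power for serious events, so there is no figure to reproduce. The counts below are assumptions, chosen to show a range.

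Inputs: n = 11,500 / 2 = 5,750 per group (Section I.B.1).

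Formulas:
- Per-group 95% interval, exact (Clopper-Pearson), for x events in n: lower = Beta quantile 0.025 (x, n - x + 1); upper = Beta quantile 0.975 (x + 1, n - x).
- Risk difference: RD = x1/n - x2/n.
- Miettinen-Nurminen 95% interval: the two values d solving (RD - d)² / V(d) = 1.96², where V(d) = [p1(1 - p1)/n + p2(1 - p2)/n] × 2n/(2n - 1) and p1, p2 are the maximum likelihood estimates under p1 = p2 + d.

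Example of the point difference, 12 vs 3: 12/5,750 = 0.209%; 3/5,750 = 0.052%; RD = 9/5,750 = 0.157 points.

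| Assumed events, vaccine vs placebo | Vaccine 95% CI (%) | Placebo 95% CI (%) | RD (points) | 95% CI for RD |
|---|---|---|---|---|
| 3 vs 2 | 0.011 to 0.152 | 0.004 to 0.126 | 0.017 | -0.080 to 0.122 |
| 10 vs 3 | 0.083 to 0.320 | 0.011 to 0.152 | 0.122 | -0.001 to 0.274 |
| 12 vs 3 | 0.108 to 0.364 | 0.011 to 0.152 | 0.157 | 0.028 to 0.318 |
| 80 vs 55 | 1.105 to 1.729 | 0.721 to 1.243 | 0.435 | 0.042 to 0.839 |

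The per-group intervals overlap in every row. The interval for the difference includes zero in the first two rows and excludes it in the last two, so the per-group display alone does not separate these cases. With very few events (3 vs 2) the interval still says something useful: an excess above about 0.12 points lies outside it.

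**The case against.** The strongest reply is that nothing here is an error. The safety hypothesis is only that the vaccine is generally well tolerated, with no margin, test or power attached. V.B says that formal comparisons are limited to reduce the number of tests, and VII.E warns about unadjusted safety comparisons. Describing rare serious events by group is common practice, and anyone holding the counts can compute a difference and its interval. Serious events also go to the DSMB by group.

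Most of this stands. It supports not testing. It does not support omitting the interval, because an estimate with an interval is not a test; V.B itself gives differences with intervals for events it does not test.

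A reader might go further in four ways that the SAP does not support:
- **That the comparison is never estimated.** Both incidences are reported, pooled vaccine beside placebo, so the point difference is available by subtraction.
- **That the plan judges safety by whether two intervals overlap.** It states no such rule, nor any other decision rule for serious events.
- **That the missing contrast is a strictly randomized one.** The safety groups follow the material received.
- **That injection-site events have no comparison at all.** V.B covers specific injection-site events in the NSAE substudy and tabulates severity by group. Only the severe category lacks a difference with an interval.

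Nor should one favorable pair of counts be read as a prediction: 12 vs 3 excludes zero and 10 vs 3 does not.

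**Conclusion.** The gap is real but limited. For the primary safety endpoint, for all serious adverse experiences and for severe injection-site reactions, the SAP names no interval for the vaccine-placebo difference, and the per-group intervals do not replace one. Its size cannot be stated from the SAP, which gives no serious-event rate. Under the assumed counts at 5,750 per group, the unreported interval runs from -0.080 to 0.122 points at the sparse end to 0.042 to 0.839 points at the other, and whether it excludes zero depends on the counts. These figures assume exactly equal groups with all subjects contributing; as-treated grouping and missing follow-up would shift the denominators slightly. This is a worthwhile reporting improvement, not a flaw that undermines a conclusion of the trial.

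**What to change.** Add to Section V.A the pooled vaccine minus placebo risk difference with a two-sided 95% Miettinen-Nurminen interval, presented as estimation without a p-value and in the as-treated groups that Section V already defines:

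- for serious and for vaccine-related serious adverse experiences, in all subjects in the serious-event summary;
- for severe injection-site reactions, in NSAE and United Kingdom subjects separately and combined, as Section V already requires for nonserious events because collection differs.

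Cost: one sentence in the plan and one column in two tables, using a method that the SAP already specifies. It needs no new data and spends no alpha.
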